## 10.2 Description of Study Population

Healthy, HIV-uninfected premenopausal women (N=10) will be enrolled based on the following inclusion criteria:  $\geq 18$  years of age, no clinical evidence of sexually transmitted infections (STIs), unimpaired renal function ( $>60$ ml/min; as estimated by Cockcroft-Gault), a regular menstrual cycle (defined as at least 1 day of menses occurring every 21-35 days), being willing to refrain from inserting anything rectally for 3 days prior and 7 days post biopsy visits. We have carefully considered allowance of different forms of contraception in this study and their impact on endogenous hormonal fluctuation (See section 14.7 for details).

## 10.3 Clinical Trial Experience

The UNC Chapel Hill Center for AIDS Research has considerable prior experience with the conduct of cervical, vaginal, and gastrointestinal biopsy studies in women. We recently enrolled 48 women in a phase I dose ranging study PK study (NCT01330199, clinicaltrials.gov) requiring all three types of biopsies to be performed. Prior to this study, UNC enrolled the majority of women in HPTN 066 (NCT01276600, clinicaltrials.gov) which required all three types of biopsies to be performed within 60 minutes of each other. In both cases, these biopsies were performed successfully and UNC enrolled to completion. Approximately 10 women who participated in the aforementioned study (NCT01330199), have expressed interest in participating in additional studies of the similar nature. As part of the screening and informed consent process, every participant will receive a detailed description of the procedures involved and the intensity of the protocol.

## 10.4 Study Sampling

At both sampling visits, the following samples will be collected in all participants:

1. Blood plasma
2. Serum

3. PBMCs
4. Rectal tissue biopsies
5. Rectal cell collection by cytobrush

10.5 Primary Endpoints:

TFVdp, FTCtp, dATP and dCTP concentrations in mixed rectal cells collected via cytobrush vs CD4+ T cells isolated from rectal tissue biopsies during the early (low estradiol) and late (high estradiol) follicular phases of the menstrual cycle

10.6 Secondary Endpoints:

1. Estradiol, progesterone and testosterone concentrations in serum
2. TFVdp, FTCtp, dATP and dCTP concentrations in peripheral blood mononuclear cells
3. TFV and FTC concentrations in plasma

Table 1 Sample collection and bioanalytical measurement

Matched Visit 1 and 2 Measurements	
Collection Matrix	Bioanalytical assay
PBMCs	TFVdp FTCtp dATP dCTP
Total rectal cells	TFVdp FTCtp dATP dCTP
Rectal CD4 cells	TFVdp FTCtp dATP dCTP
Plasma	TFV FTC
Serum	Estradiol progesterone testosterone
TFVdp=tenofovir diphosphate; FTCtp=emtricitabine triphosphate; dATP=deoxyadenosine triphosphate; dCTP=deoxycytidine triphosphate; TFV=tenofovir; FTC=emtricitabine	

10.7 Time to Complete Accrual

Based on our prior experience with several other pharmacokinetic studies that collected rectal tissue and samples from other matrices, we anticipate an accrual rate of two participants per month for a total recruitment time of 5 months.

## 10.8 Expected Duration of Participation

Once enrolled in the study, participants will participate in the study for approximately 2 weeks and then have a follow up visit approximately 1-14 days after the last sample is collected. No study data will be collected after the follow-up visit unless the participant has an adverse event (AE), which will be followed until resolution.

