## 5. Protocol Summary

Protocol Chair:	[name], MS
Sample Size:	10 cisgender females
Study Population:	Premenopausal healthy volunteer cisgender women between 18-49 years of age with an intact gastrointestinal tract
Study Site(s):	NC TraCS Clinical Translational Research Center at the University of North Carolina, Chapel Hill, NC USA
Study Design:	Single-center, open-label PK sampling study
Study Duration:	Women will be enrolled in the study within 42 days of screening, depending on the timing of their menstrual cycle, and then will be on active study for two weeks. A follow-up visit will occur within 14 days.
Study Products:	Truvada®
Study Regimen:	Five witnessed doses daily prior to each sampling visit
Primary Objectives:	To assess the impact of high and low in vivo estradiol exposure on PrEP nucleotide concentrations in different cellular populations of the lower GI tract
Hypothesis:	PrEP nucleotide concentrations in total rectal cells collected via cytobrush will significantly correlate with concentrations in CD4 + T cells isolated from rectal tissue biopsies regardless of in vivo estradiol exposure.
Secondary Objectives:	
To quantify the relationship between estradiol, progesterone and testosterone on PrEP nucleotide concentrations in rectal and peripheral blood mononuclear cells
 
To quantify the relationship between estradiol, progesterone and testosterone on PrEP concentrations in plasma

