## B) Study Procedure Time and Event:

Activity ↓	Screen (-42 to 0 Days)	Enrollment /Dose 1	Dosing Days	Sampling Visit 1	Dosing Days	Sampling Visit 2	Follow-up (Within 14 days)
Eligibility	X	X					
Informed Consent	X						
Review of Medical History	X	X					
History of Menses	X						
Vital Signs a	X			X		X	X
Complete Physical Examination	X						
Targeted Physical Examination				X		X	X
Virology Tests b	X						X
Pregnancy Test c	X	X		X		X	X
STD Tests d	X						
Urine Drug Test	X						
Safety Labs e	X	X					X
Medication Dosing f		X	X		X		
Blood Sampling				X		X	
Rectal Cell Collection by cytobrush				X		X	
Rectal Tissue Biopsy				X		X	
Adverse Event Assessment		X		X		X	X

- a. Vital signs include: blood pressure, pulse, respiratory rate, temperature, and weight. Height should be documented at the screening visit.
- b. Virology tests will include HIV Ag/Ab test, HbsAg, and Hepatitis C antibody at screening visit. HIV testing will be repeated at follow up, as well as anytime infection is suspected.

- c. Serum pregnancy test will be obtained at screening visit. Urine pregnancy test will be obtained at enrollment and follow up. Participants will also have urine pregnancy test prior to sampling on assigned biopsy days.
- d. Participants will be tested for the following sexually transmitted diseases: syphilis, gonorrhea, and chlamydia.
- e. Safety labs include: CBC with differential, urine drug screen, and the following serum chemistries: Na, K, Cl, CO2, BUN, SCr, glucose, Alb, total protein, AST, ALT, Alkaline phosphatase, total bilirubin. PT/INR and aPTT will be obtained at screening. CBC without differential at follow up.
- f. Member of study team will witness dose administration.

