## 14. Assessment of Safety

### 14.1 Safety Monitoring

Adverse events will be monitored throughout the study. Adverse events will be assessed formally before discharge to home at the inpatient visit, after each outpatient visit and at the follow-up visit during which participants will answer standardized questions regarding to prompt reporting of adverse events associated with the study medication and procedures. The research coordinator will contact participants the day following all biopsy procedures.

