#### 14.3 Adverse Events Definition and Reporting Requirements

An adverse event (AE) is defined as any untoward medical occurrence in a clinical research participant administered an investigational product and which does not necessarily have a causal relationship with the investigational product. As such, an AE can be an unfavorable or unintended sign (including an abnormal laboratory finding, for example), symptom or disease temporally associated with the use of an investigational product, whether or not considered related to the product. This definition is applied to all the study groups and is applied to all groups beginning from the time of consent. The term “investigational product” for this study refers to all study products. Study participants will be instructed to contact the study site staff to report any AEs they may experience at any time between consent and follow-up. In the case of a life-threatening event, they will be instructed to seek immediate emergency care. Where feasible and medically appropriate, participants will be encouraged to seek evaluation where the study clinician is based, and to request that the clinician be contacted upon their arrival. Study staff will obtain written permission from the participant to obtain and use records from non-study medical providers to complete any missing data element on a CRF related to an adverse event. All participants reporting an untoward medical occurrence will be followed clinically,

until the occurrence resolves (returns to baseline) or stabilizes.

The study physician will determine AE resolution or stabilization in their best clinical judgment. Study site staff will document in source documents all AEs reported by or observed in enrolled study participants regardless of severity and presumed relationship to study product. Study staff will record all AEs on case report forms.

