### 15.2 Discontinuation of Study Product in the Presence of Toxicity

Stopping rules have been created to protect the health and safety of study participants. If a single subject experiences a Serious Adverse Event, enrollment will be held while the protocol undergoes review. If 2 or more participants experience Grade 3 or Grade 4 adverse events, enrollment will be held while the protocol undergoes review.

Any Grade 3 or 4 or serious adverse event related to a study intervention (blood draw, biopsy) or the study drug will result in subject discontinuation. Participants who are withdrawn for safety reasons will complete a follow-up visit within 14 days the last sample collection visit.

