#### 3. **Anoscopy with rectal biopsy and cells:**

This is a commonly practiced medical procedure and the procedures done in this trial will not involve any unusual risks or discomforts. The risks associated with these procedures include mild discomfort and the feeling of having a “bloated stomach.” Anoscopic biopsies are painless and heal quickly (usually within three days). On extremely rare occasions, the procedure or biopsies may lead to pain, infection (sepsis), bleeding or perforation of the

gastrointestinal tract. Perforation occurs approximately once out of every 100,000 procedures. If this extremely rare complication occurs, antibiotics and surgery to repair the perforation may be necessary.

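### Minor: the closing visit may fall about one day after the last biopsies, so women seen on day 1 or 2 are not actively asked about adverse events for the rest of the usual three-day healing time

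*Combined protocol and SAP*

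**What the plan says.** Section 10.8 sets the only lower limit on the closing visit: participants will "have a follow up visit approximately 1-14 days after the last sample is collected". The same section ends study data collection at that visit, except that an adverse event is followed until it resolves.

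The other places that mention the window give only its upper end. Section 5 says "A follow-up visit will occur within 14 days", and the schedule in Section 6 B gives the same limit. Section 15.2 says "Participants who are withdrawn for safety reasons will complete a follow-up visit within 14 days the last sample collection visit".

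On contact after the biopsies, Section 14.1 states: "The research coordinator will contact participants the day following all biopsy procedures". Sections 12.5 and 13.4 describe the same next-day contact, and 13.4 allows it in person or by telephone. Section 14.3 instructs participants to "report any AEs they may experience at any time between consent and follow-up".

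On biopsy risk, Section 19.4, item 3, states: "Anoscopic biopsies are painless and heal quickly (usually within three days". It adds: "On extremely rare occasions, the procedure or biopsies may lead to pain, infection (sepsis), bleeding or perforation" of the gastrointestinal tract, and puts perforation at about 1 in 100,000 procedures.

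**The concern.** Each woman has 10 rectal biopsies at Visit 1 and 10 more at Visit 2. The first set has a late check built in, because Visit 2 includes its own adverse event assessment. For the second set, the closing visit is the only planned assessment later than the next-day contact, and Section 10.8 lets it take place on that same day.

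A complication of the second biopsies that starts after a day-1 or day-2 closing visit would come to notice only if the woman reported it herself. By then the reporting period in Section 14.3 would have ended. These are healthy volunteers with no direct benefit. Section 15.2 also holds enrollment after one serious adverse event, or after Grade 3 or 4 events in two or more participants. With 10 women, those rules depend on events being found.

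**Working it through.** The plan gives no figure of its own to reproduce. The check is a day count on its schedule, taking the day of the last biopsies (Visit 2) as day 0.

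**Inputs**
- Closing visit on day d, with d from 1 to 14 (10.8).
- Planned adverse event questioning after the last biopsies: before discharge on day 0 (13.4), on day 1 (12.5, 13.4, 14.1) and at the closing visit (6 B, 14.1).
- Usual healing time: 3 days (19.4, item 3).
- Women: 10 (5, 16.3).
- Perforation: about 1 per 100,000 procedures (19.4, item 3).

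**Days without planned questioning**

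The last planned contact is the closing visit on day d, because the day-1 contact falls on or before it. Usual healing days left after it = max(0, 3 − d).

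| Closing visit | Last planned contact | Healing days left |
|---|---|---|
| Day 1 | Day 1 (same day as the next-day contact) | 3 − 1 = 2 of 3 |
| Day 2 | Day 2 | 3 − 2 = 1 of 3 |
| Days 3 to 14 | Day 3 or later | 0 of 3 |

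The gap arises on 2 of the 14 permitted days. A window of days 3-14 keeps 14 − 2 = 12 of them.

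**Women affected**

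The plan does not say when in the window visits would be booked, so the number is anywhere from 0 to 10. If visit days were spread evenly over days 1-14 (an assumption), it is 10 × 2/14 = 1.4.

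**Expected events**

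Ten second-visit procedures at the stated perforation rate give 10 × 1/100,000 = 0.0001 expected perforations. The protocol gives no rate for bleeding or infection, so no expected count can be worked out for those.

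**Comparison with the first biopsies**

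Section 10.1 places Visit 1 at about cycle days 2-5 and Visit 2 at about days 12-15. The adverse event assessment at Visit 2 therefore follows the first biopsies by 12 − 5 = 7 to 15 − 2 = 13 days. Only the second set can have its last planned check one day later.

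**Effect on the endpoints**

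All pharmacokinetic samples are taken by Visit 2, and Section 16.3 counts a woman who misses only the closing visit as evaluable. The timing of that visit does not touch the primary or secondary concentration endpoints.

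**The case against.** The strongest reply is that no requirement is breached. The sections on the window agree with one another, and the three days are a remark about usual healing in a risk section, not a monitoring period. The protocol gives no onset times for bleeding, infection or perforation, so nothing shows that day 3 would catch what day 2 misses. Section 10.2 offers another possible reference, seven days of rectal precautions after biopsy. Every woman is also actively asked at least once after going home.

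There are passive safeguards too. Women are told to contact staff and to seek care as they see fit (12.5), and a life-threatening event is to be taken straight to emergency care (14.3). Extra visits are scheduled for anyone with an adverse event (13.4), and reported events are followed until they resolve or stabilise (14.3). Consent covers what to do if a risk occurs (19.6). The exception in 10.8 can be read as allowing a late-reported event to be recorded. Finally, the closing visit carries the post-exposure safety tests, and an early visit takes them closer to the last dose.

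Much of this stands, and it keeps the point small. Day 3 is a reasonable choice, not a standard that the protocol sets. But the seven-day precaution argues for a later minimum, not for day 1. The safeguards need either a known event or a woman who reports one herself, so none of them is planned questioning. The consent form and site procedures are not in the public text. Any instructions there might prompt self-reporting, but they bear less on scheduled contacts. Moving the earliest laboratory tests from day 1 to day 3 is a delay of at most two days, inside a window that already allows 14.

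**Conclusion.** The point holds as a minor one. The plan permits a closing visit on day 1 or day 2 after the last biopsies, which leaves 2 or 1 of the 3 usual healing days without planned questioning about new adverse events. It gives no reason for needing visits that early.

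The size rests on two things. One is the use of the protocol's usual healing time as the yardstick. The other is how many women would be booked on those two days, which the plan leaves open. Very few missed events are expected. This is an inexpensive improvement in safety follow-up, not an error that threatens the study's results.

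**What to change.** For women who complete Visit 2, state the closing window as days 3-14 after the last biopsies in Section 10.8, Section 5 and the schedule in Section 6 B. Exempt women withdrawn for safety under Section 15.2, who should be seen as early as needed.

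If early visits are wanted for convenience or for laboratory timing, keep them and add one adverse event telephone contact on or after day 3. In that case, extend the reporting period in Section 14.3 and the data-collection sentence in Section 10.8 to that contact.

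The first option changes wording in three places and adds no visit; its cost is the two earliest appointment days. The second costs one call for each woman seen before day 3.

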## 10.9 Clinical Study Site

The NC TraCs Clinical Translational Research Center at the University of North Carolina, Chapel Hill, NC USA

# 11. Study Population

## 11.1 Recruitment

Our study participants will be recruited from the Chapel Hill-Raleigh-Durham area (an area with a population of approximately 3 million). We will use the following recruitment strategies:

1. Listing our study with NC TraCS's UNC Clinical Trials Searchable Database and on the Research Match Searchable Database
2. Sending IRB approved emails to the UNC-CH campus listserv
3. Posting IRB approved fliers across campus
4. Contacting a list of subjects who have expressed interest in any of our previous healthy volunteer studies

Potential participants will be given an email address or a phone number to call if they are interested, and the study coordinator conducts a brief initial IRB-approved screening interview over the phone in a private area to determine further eligibility. If the subject is potentially eligible, a screening visit is scheduled; if one or more of

the basic inclusion criteria are not met, the subject is informed that they are not eligible.

## 11.2 Subject Withdrawal

There is a low chance of participant withdrawal from the study due to the relatively short study period. If a participant does withdraw before completion of all biopsies and samples, it will be necessary to replace them in order to have a complete set of data. If a subject completes all biopsies but misses more than 1 outpatient dose it will be necessary to replace the subject in order to have a complete set of data. If a subject is unable to provide all of the serum samples because of poor vascular access or other issues it will be necessary to replace the subject in order to have a complete set of data.

## 11.3 Inclusion Criteria

1. Healthy cisgender pre-menopausal female participants between the ages of 18 and 49 years, inclusive on the date of screening (Healthy is defined as no irregular menstrual cycles or clinically relevant abnormalities identified by a detailed medical history, full physical examination, including blood pressure and pulse rate measurement, and clinical laboratory tests).
2. Regular menstrual cycles defined as at least 1 day of menses occurring every 21-35 days)
3. Estimated calculated creatinine clearance (eCcr) of at least 60 mL/min by the Cockcroft-Gault formula where:  $eCcr \text{ (female) in mL/min} = [(140 - \text{age in years}) \times (\text{weight in kg}) \times 0.85] / (72 \times \text{serum creatinine in mg/dL})$ .
4. Negative serum pregnancy test at screening
5. All participants should be using at least one of the following methods of contraception\* from the screening visit through 72 hours prior to inpatient admission (at which time the women will be asked to remain abstinent until after their follow-up visit):

- a. Non continuous systemic hormonal contraceptives that permit intermittent menstruation
  - b. IUD (non-hormonal) placed at least 1 month prior to study enrollment
  - c. Bilateral tubal ligation (Sterilization)
  - d. Vasectomized male partners
  - e. Condom + Spermicide
  - f. \*Unless engaged in sexual activity with female only sex partners or abstinent for at least 3 months prior with no intention of becoming sexually active during the study period. Any history of recent or present concomitant male sex partners will be addressed and ruled out in the context of screening participants for eligibility for the protocol
6. Evidence of a personally signed and dated informed consent document indicating that the subject has been informed of all pertinent aspects of the trial.
7. Willing and able to comply with scheduled visits, treatment plan, laboratory tests, and other trial procedures.
8. Subject must be willing to abstain from sexual intercourse, and all and intrarectal objects and products for at least 72 hours prior to Sampling #1 until study completion.
9. Subject must be HIV-1 and Hepatitis B and C negative as documented on screening labs.
10. Subject must not be actively involved in the conception process and must be non-lactating.
11. Subject must be able to swallow pills and have no allergies to any component of the study product

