#### 11.4 Exclusion Criteria

1. Evidence or history of clinically significant hematological, renal, endocrine, pulmonary, gastrointestinal, cardiovascular, hepatic, psychiatric, neurologic,

or allergic disease (including documented drug allergies, but excluding untreated, asymptomatic, seasonal allergies at time of dosing).

2. Participants with a history of hysterectomy
3. Participants who are pregnant, possibly pregnant or lactating
4. History of febrile illness within five days prior to first dose.
5. Any condition possibly affecting drug absorption (eg, gastrectomy or other significant alterations of the gastrointestinal tract)
6. A positive urine drug screen.
7. An untreated-positive test for syphilis, gonorrhea, or Chlamydia at screening.
8. Any clinically relevant laboratory chemistry or hematology result Grade 2 or greater according to the DAIDS Laboratory Grading Tables
9. Treatment with an investigational drug within 4 months preceding the first dose of study product.
10. History of regular alcohol consumption exceeding 14 drinks (1 drink = 5 ounces (150 mL) of wine or 12 ounces (360 mL) of beer or 1.5 ounces (45 mL) of spirits) per week.
11. Participation in a clinical trial involving rectal biopsies within 6 months preceding the first dose of trial medication.
12. Blood donation of approximately 1 pint (500 mL) within 56 days prior to dosing.
13. Any condition which, in the opinion of the investigator, is likely to interfere with follow-up or ability to take the study medication appropriately.
14. Unwilling or unable to comply with the dietary and concomitant drug restrictions in regard to study drug administration as outlined in the study procedures and prohibited medications sections.
15. Women utilizing continuous hormonal contraception options such as Seasonique, injectables, implants, and hormonal IUDs

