#### 13.2 Screening Visit

After providing written informed consent, potential participants may be screened for eligibility.

The screening visit will consist of the following activities:

1. Review study overview and obtain written informed consent

2. Review approved contraception options to be used during the entire study period
3. Assign Participant ID
4. Collect demographic information
5. Collect medical/menstrual history and review contraception history
6. Perform physical exam
7. Vitals (blood pressure, heart rate, respiratory rate, height, weight (Safety vitals obtained on arrival to research clinic by nursing staff may be used))
8. Obtain safety labs:
  - a. CBC with differential (includes hemoglobin, hematocrit, WBC and differential count, platelets)
  - b. Coagulation studies (PT/INR and aPTT)
  - c. Serum Chemistry Panel (Sodium, potassium, chloride, bicarbonate, blood urea nitrogen, creatinine, serum glucose, total protein, albumin, aspartate aminotransferase, alanine aminotransferase, alkaline phosphatase, total bilirubin)
9. Serum Pregnancy Test
10. Urine Drug Test (amphetamine, barbiturate, benzodiazepine, cannabinoid cocaine, methadone, opiates)
11. Virology tests (HIV antibody combo, HBsAg, Hep C Ab)
12. STI tests (syphilis, gonorrhea, chlamydia)

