#### 14.7 Pregnancy and Pregnancy Outcomes

Participation in this study requires taking a Pregnancy Category B medication outside of routine clinical care; therefore only women not intending to become pregnant will be enrolled into this study. The duration of medication dosing is short (5 days before each sampling visit) and scheduled during the early phases of the menstrual cycle (pre-ovulation); therefore the risk of unintentional *in utero* drug exposure is low. Women will be tested at screening using a serum pregnancy test (human chorionic gonadotropin; hCG) and immediately prior to enrollment and each sampling visit using a urine pregnancy test. They will be required to use at least 1 pregnancy prevention strategy during their participation in the study. These may include abstinence for 3 months preceding; monogamy with a vasectomized cisgender male or a cisgender female partner; condoms with spermicide; a non-hormonal IUD; and hormonal contraception. Because the goal of this study is to characterize nucleotide concentrations within an individual during high and low estradiol exposure, only hormonal contraception options that do not impede cycle fluctuation will be allowed. Estradiol has been well characterized in women taking traditional 21/7 hormonal contraception regimens that allow for monthly menses. While peak estradiol concentrations are slightly diminished (1.6-1.8 fold) after initiating this contraceptive regimen, estradiol's overall concentration vs time profile follows a predictable pattern similar to the pre-contraception pattern. Furthermore, peak estradiol concentrations are still 6-9 fold greater than trough concentrations during these contraceptive cycles. Therefore, we will include women utilizing a traditional 21/7 hormonal contraception regimen in this study. Since estradiol fluctuations over the contraceptive cycle are dramatically reduced by shortening the on/off interval to 23/5 days, women utilizing continuous hormonal contraception options such as Seasonique, injectables, implants, and hormonal IUDs will be excluded from this study.

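### Inclusion 5a and exclusion 15 are looser than the contraceptive rule argued in section 14.7, so a screener working from the numbered criteria could enrol a 23/5 pill user whose Visit 2 is then labelled high estradiol

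*Combined protocol and SAP*

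**What the plan says.** Section 14.7 derives the contraceptive rule from the study's aim. Its general principle is that "only hormonal contraception options that do not impede cycle fluctuation will be allowed". It then accepts one schedule, "we will include women utilizing a traditional 21/7 hormonal contraception regimen in this study", because peak estradiol on that schedule is still 6-9 fold above trough. Its closing sentence opens with "Since estradiol fluctuations over the contraceptive cycle are dramatically reduced by shortening the on/off interval to 23/5 days" and goes on to exclude continuous methods. Section 10.2 sends the reader there: "We have carefully considered allowance of different forms of contraception in this study and their impact on endogenous hormonal fluctuation".

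The numbered criteria are worded differently:

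- Inclusion 5a (section 11.3) accepts "Non continuous systemic hormonal contraceptives that permit intermittent menstruation".
- Inclusion 2 (section 11.3) asks for "Regular menstrual cycles defined as at least 1 day of menses occurring every 21-35 days".
- Exclusion 15 (section 11.4) removes "Women utilizing continuous hormonal contraception options such as Seasonique, injectables, implants, and hormonal IUDs".

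The screening list in section 13.2 includes "Review approved contraception options to be used during the entire study period".

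Estradiol exposure is assigned by timing. Section 10.1 places Visit 1 at about Days 2-5 of the cycle and Visit 2 at about Days 12-15. Section 10.5 labels these phases low and high estradiol. Section 16.1 correlates cytobrush and CD4+ T-cell concentrations within each visit.

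**The concern.** The protocol reasons its way to a limit on the hormone-free interval and then leaves that limit out of the list staff use to decide eligibility. Inclusion 5a is not merely silent. It states a rule of its own (not continuous, menses permitted), and a 23/5 pill satisfies that rule.

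What is at stake is the exposure contrast. The primary objective compares high with low estradiol, and the hypothesis is that the cytobrush correlation holds at both levels. If a woman's estradiol moves little between visits, her Visit 2 result is further evidence at low exposure but is counted as evidence at high exposure. A strong Visit 2 correlation would then say less than it appears to about cytobrush sampling when estradiol is high, which is what section 8 wants to know for people taking exogenous estradiol.

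**Working it through.** **1. The two sets of rules side by side**

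| Regimen | Section 14.7 reasoning | Inclusion 5a | Exclusion 15 |
|---|---|---|---|
| 21/7 | accepted by name | admitted | not named |
| 23/5 | said to reduce fluctuation sharply | admitted | not named |
| Continuous | excluded by name | not admitted | excluded |

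Numbered criteria: 11 inclusion + 15 exclusion = 26. Criteria stating an on/off interval: 0 of 26. The two regimens that 14.7 separates are treated alike in 11.3 and 11.4.

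**2. A 23/5 user taken through the list**

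- Inclusion 2: 23 + 5 = 28 days, inside 21-35. Met, if she bleeds in the 5-day break.
- Inclusion 5a: the method has a break and permits menses. Met.
- Exclusion 14: refers to the prohibited-medications section. Section 12.4 gives only dietary rules, so it does not catch her.
- Exclusion 15: names continuous methods. Her regimen is not among them.
- Section 11.1: the telephone screen uses the basic inclusion criteria, which do not separate 21/7 from 23/5.

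**3. What happens to her data**

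Visit 2 is labelled high estradiol by cycle day (10.1, 10.5). Replacement covers withdrawal, missed doses and missing samples (11.2), and unevaluable participants (16.3). None of these covers a failure to reach high estradiol. Section 16.1 uses no estradiol threshold. She therefore stays in as 1/10 = 10% of the Visit 2 points.

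**4. The plan's own figure**

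Section 16.2 states 80% power at n = 10 and r = 0.78. Alpha and sidedness are not stated; I assume two-sided 0.05. By the method of the cited package:

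- Critical r = sqrt(t² / (t² + n − 2)). With t = 2.306 on 8 degrees of freedom, this is 0.632; atanh(0.632) = 0.745.
- Shifted z = atanh(0.78) + 0.78/(2 × 9) = 1.045 + 0.043 = 1.089.
- Power = Φ((1.089 − 0.745) × sqrt(7)) = Φ(0.910) = 0.819.

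The result is 81.9% against the stated 80%, so the figure reproduces. It depends on n and r only. Rewording the criteria leaves n = 10, so it does not move.

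**5. Illustration of dilution (assumed inputs)**

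Suppose an unaffected woman has a Visit 2/Visit 1 estradiol ratio f of 6 to 9. This borrows the 21/7 peak-to-trough range in 14.7, which is not a measured visit ratio. Suppose a 23/5 user has a ratio g of 1 to 2; the documents give no value. With k such women among 10, the geometric-mean ratio is f^((10−k)/10) × g^(k/10).

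| k | Lowest (f = 6, g = 1) | Highest (f = 9, g = 2) |
|---|---|---|
| 0 | 6.0 | 9.0 |
| 1 | 5.0 | 7.7 |
| 2 | 4.2 | 6.7 |
| 3 | 3.5 | 5.7 |

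On these assumptions one woman dilutes the group contrast modestly, and three take it to roughly 60% of its original size (3.5/6.0 = 0.58; 5.7/9.0 = 0.63).

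**The case against.** The strongest reply is that the limit is already in force. Section 14.7 is part of the protocol, its general principle is binding, and the population description in 10.2 refers to it on exactly this question. A careful screener who reads both would refuse a 23/5 user. The contraception review in 13.2 and the eligibility reviews in 17.1 give further chances to catch her. One can also argue that the list in exclusion 15 is illustrative and that 14.7, by giving the 23/5 evidence as its reason, places shortened-interval pills in the excluded class.

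Much of this stands. A reader might infer that the protocol as a whole admits 23/5 users; it does not, and on balance it points against enrolling them. But the protection is incomplete. The closing sentence of 14.7 moves from 23/5 evidence to an exclusion worded for continuous methods only, and a pill with a 5-day break is not naturally called continuous. Neither 13.2 nor 17.1 says which interval is acceptable, and 11.3 and 11.4 do not refer to 14.7.

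The second reply is that no result is shown to be wrong. The planned test is a correlation within a visit, and a woman with low Visit 2 estradiol still supplies a valid matched pair. This stands for the correlation coefficient. It does not answer the problem with the label put on that correlation.

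The third reply is that a flat profile would be seen, because serum estradiol is measured at both visits and a secondary objective relates it to nucleotides. That is correct. The remaining gap is that 16.1 names no analysis or display that brings those values to bear on the by-visit correlations.

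**Conclusion.** The point holds as a mismatch between the eligibility list and the protocol's own rationale, and it is worth correcting. The list lets through a regimen that 14.7 says undermines the estradiol fluctuation on which the primary objective depends, and nothing later in the plan relabels or replaces such a woman.

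The size cannot be computed: the documents give neither the number of 23/5 users likely to enrol nor their change in estradiol between visits. The firm quantities are 0 of 26 criteria stating an interval, a 28-day cycle inside the accepted range, and 10% of the Visit 2 points per woman. The dilution figures rest on assumed ratios and show only the order of magnitude.

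A reader might go further and infer that the Visit 2 correlation is biased or that power is lost. The documents support neither: no direction of effect on r can be derived, and the stated power reproduces with n unchanged. The harm is to the interpretation of Visit 2 as a high-exposure result, and it arises only if such a woman is actually enrolled.

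**What to change.** - **Inclusion 5a:** limit hormonal methods to *traditional 21/7 hormonal regimens (see 14.7)*.
- **Exclusion 15 and the last sentence of 14.7:** extend both to *continuous or shortened hormone-free-interval regimens (such as 23/5)*, so that the three places agree.
- **Section 13.2:** record the on/off schedule at the contraception review.
- **Section 16.1:** report each woman's measured Visit 1 and Visit 2 serum estradiol alongside the by-visit correlations, so the reader can see whether the labels fit.

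I would not add a sensitivity analysis that drops women whose estradiol failed to rise (a Visit 2/Visit 1 ratio of 1 or less). Section 14.7 describes fluctuation on 23/5 as reduced, not abolished, so a user with a small rise would pass that cut-off. It would also remove women who show no rise for other reasons, such as visit timing.

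The cost is wording in two criteria and one sentence of 14.7, one case report form field, and one descriptive listing from serum already collected. No samples or visits are added. A few pill users become ineligible, which may slightly slow the planned accrual of two participants per month.
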